### 3 INTRODUCTION

The 2021 European Society of Cardiology guidelines recommend cardiac pacing in patients aged >40 years with tilt-induced asystolic reflex syncope (class I, level of evidence A). (1) The recommendation relies on recent results from the multicentre, randomised, double-blinded, parallel-design BIOSync trial. (2) The BIOSync study provided evidence of benefit of dual-chamber pacing in patients with tilt-induced reflex syncope and confirmed the role of Head-up Tilt Table (HUTT) test as a diagnostic method for cardiac pacing in reflex syncope. The study randomised patients aged  $\geq 40$  years with frequent reflex syncope and VASIS 2B cardio-inhibitory response to HUTT to receive either an active or an inactive dual-chamber pacemaker with the CLS pacing mode. The rationale for pacing with CLS in cardioinhibitory reflex syncope was recently reviewed by Tomaino et al. (3) CLS is able to measure changes in intracardiac impedance during the systolic phase of each cardiac cycle which are strictly correlated to the increased heart rate and right ventricular contraction speed which are usually present during the pre-syncope phase of the reflex. It was hypothesized that an early onset of CLS pacing may be triggered by the compensatory increase in heart rate to counteract vasodilation and pressure drop during the pre-syncope phase of the reflex. The BIOSync study showed a 77% reduced risk of syncope in the DDD-CLS group as compared to pacing off. The design of the BIOSync study did not allow to assess the specific effect that CLS adds to dual-chamber pacing. Despite DDD-CLS pacing, 22% of patients had syncopal recurrence in 2 years. Further investigations are therefore needed in order to reduce this failure rate. Indeed, it is still unclear whether syncopal recurrences should be ascribed to dominant vasodilation or if the CLS programming/functioning needs optimization to more adequately sustain cardiac output during reflex in these specific cases. (3) The purpose of this study is to explore changes in hemodynamic parameters during HUTT and their timing with respect to CLS pacing activation. This study may add knowledge to better understand the mechanisms underlying recurrent syncopal events and optimal pacing programming.

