### 4.5 Description of the CLS algorithm

The CLS algorithm was developed to provide a physiologic pacing rate modulation in response to metabolic demand and it is based on an analysis of the right ventricle unipolar impedance trend during systole. Impedance trend is obtained by sampling with high frequency subthreshold pulse train: an increase of the impedance trend slope, with respect to a (rest) reference, is an indication of an increased metabolic demand and it is used to adapt heart rate accordingly. In particular, impedance changes depend on the amount of blood and myocardial tissue in the volume surrounding the tip of the right ventricular lead. During contraction, blood ejection causes tighter electrode contact with myocardial tissue (involving a larger proportion of tissue relative to blood volume), leading to a progressive impedance increase towards late systole (3). CLS automatically increases pacing rate in response to detected changes in myocardial contractility. CLS functioning actively interacts with the autonomic regulation

process of cardiac output, occurring under several conditions of everyday life, not limited to exercise. (4)

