#### 8.1.3 Data of interest

- a) Heart rate, blood pressure, stroke volume, and peripheral resistance will be collected at the following time-points during HUTT:
  - time of maximum spontaneous heart rate (end of phase 1/beginning phase 2 of the reflex);
  - time of pacing onset;
  - time of recovery of spontaneous rhythm after pacing (end of recovery period);
  - time of syncope (i.e. loss of consciousness) during HUTT (also assessed by video recording if available at investigational site)
  - time of tilt-down (supine patient position just after tilt-down)
- b) Above-mentioned times of interest (expressed in HH:MM:SS from the start of the HUTT)
- c) Duration of the recovery phase (interval from maximum pacing rate to basic rate or spontaneous rhythm expressed in MM:SS from the start of the HUTT)
- d) Slopes in heart rate (bpm per sec) and systolic blood pressure (mmHg per sec) during the recovery phase

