#### **Definitions.**

Phase 1 of reflex during HUTT is defined as the interval from the start of blood pressure decrease due to a reduced venous return (and consequent corrective heart rate increase) to the beginning of phase 2.

Phase 2 is characterized by decrease of heart rate due to the activation of vagal reflex. Phase 2 (HR drop) may be partially masked by pacing activation.

Recovery phase is defined as the interval from maximum pacing rate to basic rate or spontaneous rhythm, if pacing is not delivered.

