**Table 2 – Device programming**

Parameter	
Pacing Mode	DDD-CLS
Basic rate	50 bpm
Maximum CLS rate	120 bpm
Upper tracking rate	130 bpm
Atrioventricular delay	Low; 180–140 ms
Atrioventricular hysteresis mode	IRSplus
CLS Resting Rate Control	OFF
Atrial pacing polarity	Unipolar
Ventricular pacing polarity	Unipolar

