10.2 HUTT

Data file: Identifier patient_ display_id_full	Notes	Variable name	Variable label	Variable level	Nominal values
hutt	Case listing	CVMHRITM	Time of maximum spontaneous heart rate (end of phase 1/beginning phase 2 of the reflex)	Scale	n.a.
	descriptive	QSHUPMPC	Did the pacemaker pace during HUTT?	nominal	o Yes o No
	Case listing	PRPCSTTM	Time of pacing onset/maximum pacing rate	scale	n.a.
	Case listing	PRHRPCTM	Time of recovery of basic pacing rate or spontaneous rhythm after pacing (end of recovery period)	Scale	n.a.
	Case listing	PRHRHRTM	Time of recovery of starting spontaneous heart rate	Scale	n.a.

		(for QSHUPMPC = No)			
descriptive	QSHUSNC	Did syncope (i.e. loss of consciousness) occur during HUTT?	Nominal	n.a.	
Case listing	QSSNCTM	Time of syncope	Scale	n.a.	
Case listing	QSTDTM	Time of tilt-down (supine patient position just after tilt-down)	scale	n.a.	
descriptive	QSHRHRDU	Duration of the recovery phase (interval from maximum pacing rate to basic rate or spontaneous rhythm from the start of the HUTT) [sec]	Scale	n.a.	
descriptive	CVHRHUST	HR at HUTT start [bpm] (upright patient position just after tilt)	Scale	n.a.	
descriptive	CVMHRT	HR at time of maximum spontaneous heart rate (end of phase 1/beginning phase 2 of the reflex) [bpm]	Scale	n.a.	
descriptive	CVHRPC	HR at time of pacing onset/maximum pacing rate [bpm]	Scale	n.a.	
descriptive	CVHRAPC	HR at time of recovery of basic pacing rate or spontaneous rhythm after pacing (end of recovery period) [bpm]	Scale	n.a.	
descriptive	CVHRAPCN	HR at time of recovery of basic pacing rate or spontaneous rhythm after pacing not applicable	nominal	o True o False	
descriptive	CVHRHU	HR at time of syncope during HUTT [bpm]	Scale	n.a.	
descriptive	CVHRAHU	HR at time of tilt-down	Scale	n.a.	
descriptive	CVSBPHST	Systolic BP at HUTT start [mmHg]	Scale	n.a.	
descriptive	CVDBPHST	Diastolic BP at HUTT start [mmHg]	Scale	n.a.	
descriptive	CVSBPMHR	Systolic BP at time of maximum spontaneous heart rate (end of phase 1/beginning phase 2 of the reflex) [mmHg]	Scale	n.a.	
descriptive	CVDBPMHR	Diastolic BP at time of maximum spontaneous heart rate (end of phase 1/beginning phase 2 of the reflex) [mmHg]	Scale	n.a.	
descriptive	CVSBPPC	Systolic BP at time of pacing onset/maximum pacing rate [mmHg]	Scale	n.a.	
descriptive	CVDBPPC	Diastolic BP at time of pacing onset/maximum pacing rate [mmHg]	Scale	n.a.	

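### One set of SAP fields covers both pacing onset and maximum pacing rate; where the two differ, either the onset values or the recovery slopes are not those the protocol defines

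*SAP*

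**What the plan says.** Protocol 8.1.3, item (a), lists the instants at which heart rate (HR), blood pressure, stroke volume (SV) and peripheral resistance (TPR) are collected. The pacing instant in that list is the "time of pacing onset". Maximum pacing rate is not in the list.

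Item (c) of the same section gives the duration of the recovery phase as the "interval from maximum pacing rate to basic rate or spontaneous rhythm". The Definitions that follow say the same: "Recovery phase is defined as the interval from maximum pacing rate to basic rate or spontaneous rhythm, if pacing is not delivered". Item (d) asks for slopes in HR and systolic blood pressure (SBP) over that phase.

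SAP 10.2 has one time variable, PRPCSTTM, labelled "Time of pacing onset/maximum pacing rate". It has one matching set of values: CVHRPC (HR), CVSBPPC and CVDBPPC (systolic and diastolic pressure), CVSVPC (SV) and CVTPRPC (TPR). Their labels join the same two events with a slash. The recovery duration, QSHRHRDU, is a separate variable and its label names only the maximum: "interval from maximum pacing rate to basic rate or spontaneous rhythm from the start of the HUTT". The slopes SLOPE_HR_HUTT_SAR and SLOPE_SBP_HUTT_SAR appear with a label and no visible formula.

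**The concern.** The protocol uses two events for two purposes. Onset values describe the haemodynamic state when closed-loop stimulation (CLS) began to pace. Maximum-rate values are the starting point of the recovery slopes. One entry can serve both purposes only if the two events fall at the same instant.

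This touches the core of the study. Its objective is haemodynamic change and its timing relative to CLS activation, and the Introduction rests on the hypothesis that "an early onset of CLS pacing may be triggered by the compensatory increase in heart rate to counteract vasodilation and pressure drop". If the fields hold the maximum, the time of onset and all five onset values are lost. If they hold onset, the slopes start from the wrong values. If sites read the label differently, a mean and standard deviation would mix two events. In each case a reader of the report could not tell which event a value describes.

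**Working it through.** The plan states no figure on this point, and Protocol 12.5 says the sample size does not rest on a calculation, so there is nothing to reproduce. The check is a mapping of definitions, followed by algebra.

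**1. Mapping protocol items to SAP fields**
- Fields hold onset: item (a) is met. HR and SBP at the start of the recovery phase have no field, so the item (d) slopes lack their start values.
- Fields hold the maximum: the slopes can be formed. The onset time and the five onset values are missing.
- Onset and maximum coincide: both items are met.

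**2. Do the documents make them one instant?** The same table uses a slash to join the end of phase 1 to the beginning of phase 2. There the Definitions support it, because phase 1 is defined as running until phase 2 begins. No definition equates pacing onset with maximum pacing rate. Protocol 4.5 states that "CLS automatically increases pacing rate in response to detected changes in myocardial contractility", so the events can differ in principle. That does not show that they differ in any given test.

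**3. Could the slopes draw on other data?** SAP chapter 4 lists only exports from the clinical database, and no continuous monitor file. SAP 2.4 provides a category for variables needed only to build derived ones, but no HR or SBP at maximum rate appears under it. The time of maximum rate might be recovered as PRHRPCTM − QSHRHRDU; that yields no HR, pressure, SV or TPR value.

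**4. Size for the HR slope (algebra)**
- Slope over the protocol's recovery phase: (HRend − HRmax)/D, where D is the recovery duration.
- Slope if onset HR is the start value and D is correct: (HRend − HRonset)/D.
- Proportion by which it is too flat: (HRmax − HRonset)/(HRmax − HRend). D cancels.

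Table 2 gives a basic rate of 50 bpm and a "Maximum CLS rate" of 120 bpm. These are settings, not observed values. Recovery may also end in spontaneous rhythm, and no onset rate is given. With assumed rates:
- end 50, maximum 120, onset 120: 0/70 = 0%
- end 50, maximum 120, onset 100: 20/70 = 29%
- end 50, maximum 120, onset 80: 40/70 = 57%
- end 70, maximum 120, onset 90: 30/50 = 60%

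The result follows the chosen inputs, so no percentage range can be given as a bound. If D were itself counted from onset, the slope would be flatter still. For example, with onset 100, an assumed 120 s of recovery and 30 s from onset to maximum, −50/150 = −0.33 bpm/s replaces −70/120 = −0.58 bpm/s.

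**5. Size for the SBP slope.** The shift is (SBPmax − SBPonset)/D, and its sign is unknown. Each 10 mmHg between the events shifts the slope by 10/60 = 0.17 mmHg/s for an assumed 60 s, or 10/120 = 0.08 mmHg/s for an assumed 120 s.

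**6. A consistency check.** Compare PRPCSTTM with PRHRPCTM − QSHRHRDU. If the true gap is zero and all three entries are rounded to whole seconds, the combined rounding error is at most 1.5 s. The computed gap is a whole number, so it is −1, 0 or 1. Rounding therefore cannot explain a gap of 2 s or more. The choice of instant on a plateau, or reading one time from the ECG and another from the monitor, could.

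**The case against.** The strongest reply is that the slash denotes one instant, as it does elsewhere in the same table. Item (a) passes from pacing onset straight to the end of recovery without listing maximum rate, so the SAP label may simply join items (a) and (c). This reading is possible. However, unlike the phase 1/phase 2 label, no definition supports it, and the SAP names the maximum alone in QSHRHRDU. Part of the gap does start in the protocol: item (d) needs values at an instant that item (a) does not list.

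The second reply is that the CRF user guide or the execution-phase source data sheet may say what to enter, and that a slope formula may stand in a table part not shown. This stands as a limit. Neither the guide nor the sheet was supplied. The absent formula alone would be missing detail, although SAP 2.4 asks for construction instructions.

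Third, the study is descriptive, with no hypotheses and at most 20 patients. That limits the consequences, but these values and slopes are the data the study exists to produce.

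A reader might go further and infer that the SAP cannot deliver both items in any patient, or that the slopes will be wrong by a known percentage. The documents support neither inference, because they do not say how often, or by how much, the events differ. Nor should a reader infer that the recovery duration is safe. QSHRHRDU is labelled as starting at maximum rate, but nothing says it was measured independently of PRPCSTTM.

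**Conclusion.** The point holds conditionally. As written, SAP 10.2 gives the protocol's onset values and the protocol's slope start values together only where pacing onset and maximum pacing rate coincide. The documents neither state that they do nor say which event is entered. Where they differ, one of the two items is not the one the protocol defines; where they coincide, nothing is wrong.

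The size is known only as algebra: (HRmax − HRonset)/(HRmax − HRend) for the HR slope, assuming a correct duration, and zero when the events coincide. This is a cheap improvement. Confidence is medium because unsupplied data-collection documents might settle which event is entered.

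**What to change.** 1. Define PRPCSTTM, CVHRPC, CVSBPPC, CVDBPPC, CVSVPC and CVTPRPC as pacing onset, as item (a) requires.
2. Add three fields: time, HR and SBP at maximum pacing rate. Tie them to one stated instant, for example the last beat at the maximum rate before the rate starts to fall. They can be read from the continuous monitor recording (Protocol 9.2.3) or, for time and HR, from the ECG trace (Protocol 9.2.3.1). At 5 mm/s a beat at 120 bpm spans only 2.5 mm (0.5 s × 5 mm/s), so the monitor is the better source for HR.
3. Write the slopes out, with the duration taken from the same two times: (CVHRAPC − HR at maximum)/duration and (CVSBPAPC − SBP at maximum)/duration. Give neither slope where the recovery end-point is not applicable (CVHRAPCN = True). Report patients without pacing (QSHUPMPC = No) separately, using PRHRHRTM. They should be neither dropped nor pooled with the paced slopes, and the SAP should name their start point, since they have no maximum pacing rate.
4. If the sponsor holds that the events always coincide, state this and confirm it for each patient on the recording. A gap of 2 s or more between PRPCSTTM and PRHRPCTM − QSHRHRDU is a prompt to re-check, not proof. A match shows only that the maximum-rate time was entered, so the onset still needs confirming. The check is informative only if QSHRHRDU was measured independently of PRPCSTTM.

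The cost is three fields, a re-read of retained recordings in at most 20 patients (Protocol 8.2.7) and a SAP update, which the SAP allows before database freeze. An amendment may also be needed, because Protocol 14 treats changes that affect procedures or data analysis as substantial. Where recordings were not kept, the SAP should state which event the field holds and report the other item as not available.

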9.2.3 Head-up tilt test

The HUTT will be performed according to the Italian protocol (9) and patient's hemodynamics will be continuously monitored during the entire test. Specifically, an external monitor will be used for continuous measurement and recording of systolic and diastolic BP, HR, SV, and TPR.

Prior to the start of the HUTT, a trained member of the study team will prepare the patient and set up the equipment needed for the test as follows:

- patient shall be supine on the tilt table and secured to it with the BP sensor cuff of the external monitor on his/her finger. Hand wearing the pressure sensor shall be placed on the chest at about 10 cm from heart and held in this position throughout the test;
- ECG leads shall be placed on patient’s chest and a BP cuff on his/her arm;
- If used, a high-definition camera may be placed to contemporarily pick up both patient and the external monitor positioned close to the tilt table.

**Note: video recordings of the entire test shall not be provided to the Sponsor and will be destroyed immediately after the examination. The investigator will assess the time of symptoms onset and will report it in the CRF.**

After 10 minutes in supine position, the patients will be tilted to 70° using an electronically operating tilt-table with a footboard.

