2.4 General information

This SAP may contain verbatim excerpts from the version of the CIP specified at the cover sheet. Such excerpts are *italicized with light blue background*.

The main aspects and the design of the clinical investigation are presented in chapters 3-4.

General statistical procedures are summarized in chapter 5. Those methods are used in case there is no other specification within this document.

Analysis set(s) and other global variables are defined in detail in chapter 6.

Descriptive and inferential statistical analyses for endpoint(s) are handled in following chapters. Thereby the following statistical considerations are specified:

- Analysis set: Definition of the analysis population (e.g. Intention-to-Treat or Per-Protocol for controlled clinical investigations or all patients with valid informed consent for single-arm clinical investigations)
- Variable characteristics: Description of all relevant variables (directly addressable from validated tools, e.g. CDMS or CDW, and derived variables) such as variable name, variable label, variable values, and data type.
- Derived variables, if applicable: For variables, which are not directly addressable from validated tools but are derived from other variables, pseudo-code or other instructions for the variable construction shall be provided.
- Missing, unused or spurious data: Specification of all data to be excluded from the specific analysis, e.g. data measured after a pre-specified point in time or implantation date after pre-hospital discharge date; specification whether and –if applicable- how to impute missing data.
- Data analysis: Description of descriptive, exploratory, and confirmatory analyses in text, tables, or pseudo-code shall be provided for unambiguous data analysis.

All variables are defined in tables using the following columns:

Data file: Name of a data file exported from the CDMS and unique identifier, if applicable (e.g. patient-specific "patient_display_ID_full" or event-specific record_ID); new data files ("data_SAR") may be generated by merging all relevant data from the original CDMS data files and generating derived variables;

Notes: Information whether data shall be presented with "descriptive" methods as defined in this SAP, data for "case listings" of original data for each patient specified, or "no report" for data needed for generating derived variables only;

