3.1 Objective(s)

CIP chapter 7.1

The purpose of this study is to add knowledge to better understand the hemodynamic mechanisms underlying recurrent syncopal events and optimal pacing programming.

CIP chapter 7.2

This study will provide standardized, complete and quality controlled data sets with parameters that describe hemodynamic changes and their timing with respect to CLS pacing activation during reflex syncope induced by HUTT.

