12.14 Exploratory analysis and sensitivity analysis

Not applicable.

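### Outside the recovery phase, SAP 10.2 summarises no within-patient change and no interval around pacing onset, and six of its fields merge pacing onset with maximum pacing rate

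*SAP*

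**What the plan says.** The protocol's Introduction gives the aim: "The purpose of this study is to explore changes in hemodynamic parameters during HUTT and their timing with respect to CLS pacing activation". SAP 3.1 repeats the objective as data sets with "parameters that describe hemodynamic changes and their timing with respect to CLS pacing activation during reflex syncope induced by HUTT".

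Protocol 8.1.3 turns this into a list: heart rate, blood pressure, stroke volume and peripheral resistance at five time-points; those times counted from the start of the test; the recovery duration; and the heart rate and systolic pressure slopes during recovery. One of the five time-points is the "time of pacing onset". The definitions that follow start the recovery phase at a different event: "Recovery phase is defined as the interval from maximum pacing rate to basic rate or spontaneous rhythm, if pacing is not delivered".

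SAP 10.2 carries the whole list and adds levels at the start of the test. It marks every level 'descriptive' and every event time 'Case listing'. SAP 2.4 keeps the two apart: case listings are "of original data for each patient specified", and descriptive items are summaries. For the pacing event there is one time field, "Time of pacing onset/maximum pacing rate" (PRPCSTTM), and one value field per parameter with the same double label (CVHRPC, CVSBPPC, CVDBPPC, CVSVPC, CVTPRPC). SAP 12.14, "Exploratory analysis and sensitivity analysis", is marked not applicable.

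**The concern.** A question about change and timing is answered within patients: how far pressure, stroke volume and resistance moved in each patient, and how long before or after pacing began. Separate summaries at each time-point do not show this. If the same patients contribute to two points, the difference of the means is the mean change, but how much patients differ in that change, and how precisely the mean is known, is missing. Intervals can be worked out by hand from the listed times. Haemodynamic changes cannot, because the levels are not listed.

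The merged label is a separate problem. Protocol Table 2 sets a basic rate of 50 bpm and a maximum CLS rate of 120 bpm, so the first paced beat and the peak paced rate need not coincide. A reader of the report could not tell which event a 'pacing' value describes. Recovery duration (QSHRHRDU) and both slopes start at maximum pacing rate, which has no field of its own. SAP 2.4 asks for pseudo-code or instructions for derived variables, yet 10.2 gives no slope formula. The ambiguity may therefore reach the only within-patient measures that are planned.

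**Working it through.** The plan states no figure to reproduce: protocol 12.5 says that the sample size of 20 was not calculated. The check is a row count of SAP 10.2, followed by an illustration of what the missing summaries would carry.

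**Row count, SAP 10.2**

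| Type of row | Rows | Marked |
|---|---|---|
| Levels: 5 parameters (HR, systolic BP, diastolic BP, SV, TPR) x 6 points | 30 | descriptive |
| Event times | 6 | case listing |
| Yes/no or not-applicable flags | 3 | descriptive |
| Recovery duration | 1 | descriptive |
| Recovery slopes (HR, systolic BP) | 2 | descriptive |
| Comment field | 1 | case listing |
| Total | 43 | |

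- Within-patient measures: 1 + 2 = 3, all in the recovery phase.
- Changes between time-points outside recovery: 0.
- Summarised intervals to or from pacing onset: 0.
- Diastolic BP, SV and TPR: no within-patient measure in any phase.
- Fields with the double pacing label: 1 time + 5 values = 6.

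**Spread and precision of a change**

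Assume that two levels have the same SD, s, and a within-patient correlation r. The documents give neither. The report would show the SDs but not r.

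SD of change = s x sqrt(2(1 - r)).

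95% half-width of the mean change = t(0.975, n - 1) x SD of change / sqrt(n), the t-based interval of SAP 12.3. At n = 20 the multiplier is t(0.975, 19)/sqrt(20) = 0.468.

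| r (assumed) | SD of change | Half-width, n = 20 |
|---|---|---|
| 0 | 1.41s | 0.66s |
| 0.5 | 1.00s | 0.47s |
| 0.8 | 0.63s | 0.30s |
| 0.9 | 0.45s | 0.21s |

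The ends differ about threefold. If s were 15 mmHg (assumed), they would be 9.9 and 3.1 mmHg. The same reported means and SDs fit every row of this table.

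Pairs that need pacing or syncope use only the patients who had that event, so n is smaller. The multiplier is 0.554 at n = 15, 0.715 at n = 10, 1.049 at n = 6 and 1.591 at n = 4. At n = 10 the range is 0.715 x 1.41s = 1.01s down to 0.715 x 0.447s = 0.32s. How many patients will be paced or will faint is not known.

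**The case against.** The strongest reply is that SAP 10.2 does what the protocol asks. Protocol 8.1.3 requests no differences and no onset-based intervals, the objective is to provide data sets, and there are no endpoints or hypotheses. This stands in part: a reader might infer that the SAP breaches 8.1.3, and it does not. The gap is against the stated purpose, and it begins in the protocol's own list.

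A second reply is that nothing is lost. Per-patient values stay in the exported and archived database, event times are listed for at most 20 patients, SAP 12.3 allows inferential methods, and SAP 12.15 allows updates before database freeze. This also stands as a limit on the harm: the shortfall is in the planned report, not in the data. But neither SAP section specifies a paired summary.

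A reader might also infer that comparing the mean at syncope with the mean at the start of the test would be biased, because non-fainters are in only one of them. That comparison would mix change with patient selection, but the SAP does not plan it, so it is not an error in the planned analysis.

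Finally, the slash may mean 'whichever event the site recorded'. That does not help, because no second field shows which one it was. Nor does it show that the recovery duration or slopes will be wrong, only that their starting point is not pinned down.

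**Conclusion.** The point holds as a shortfall against the stated purpose. The planned report gives no summarised interval to or from pacing onset and no spread for any change before recovery, and diastolic BP, SV and TPR have no within-patient measure at all. The merged label is a plain inconsistency with the protocol and leaves the reference point of every pacing value open, and possibly the start of the recovery measures.

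The row counts need no assumption. The half-width range of 0.66s to 0.21s at n = 20 rests on equal SDs and an assumed correlation of 0 to 0.9. It shows that the missing information matters; it does not predict the result. The change should be made before database freeze. The study remains usable without it.

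**What to change.** 1. State which event the six merged fields hold, and which event starts QSHRHRDU and the two slopes. Where the other event is needed, take its time and heart rate from the ECG traces (protocol 9.2.3.1), and BP, SV and TPR from the monitor recording if retained; protocol 9.2.3 says that "an external monitor will be used for continuous measurement and recording of systolic and diastolic BP, HR, SV, and TPR". Otherwise report it as unavailable.
2. Add two derived descriptive variables: the signed per-patient intervals from maximum spontaneous heart rate to pacing onset, and from pacing onset to syncope.
3. Add per-patient changes in the five parameters for four pairs: test start to maximum heart rate; maximum heart rate to pacing onset; pacing onset to syncope; and maximum heart rate to syncope, so that unpaced fainters are covered. Use only patients with both values, give n and the t-based interval of SAP 12.3, and run no tests.
4. Case-list the 30 levels with each patient's pacing and syncope status. With at most 20 patients this serves better than summaries split by outcome.

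Two cautions belong in the interpretation only: fainters are tilted down at loss of consciousness and may recover supine, and SAP 10.2 has no nitroglycerine variable.

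Cost: 2 intervals, 5 x 4 = 20 changes and one listing, all exploratory and unadjusted, with wide intervals where few patients were paced or fainted. The derivations use collected fields. However, 2 intervals and 2 x 5 = 10 changes are anchored on pacing onset and depend on the answer to item 1. That may need a query per paced patient, and some BP, SV and TPR values may not be recoverable.
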